8.1.2. Serious Adverse Events (SAE)

A serious adverse event is any untoward medical occurrence that at any dose:

- results in death,
- is life-threatening,
- requires hospitalization or prolongation of existing hospitalization,
- results in persistent or significant disability/incapacity, or
- is a congenital anomaly/birth defect.

Important medical events that may not result in death, be life-threatening, or require hospitalization may be considered an SAE when, based upon appropriate medical judgment, they may jeopardize the safety of the subject, and may require medical or surgical intervention to prevent one of the outcomes listed in this definition. Examples of such events are intensive treatment in an emergency room or at home for allergic bronchospasm, blood dyscrasia, or convulsions that do not result in hospitalization.

Note:

- The term "life-threatening" refers to an event in which the subject was at risk of death at the time of the event; it does not refer to an event which hypothetically might have caused death if it was more severe.
- Inpatient hospitalization is considered to have occurred if the subject has had to stay in hospital overnight. The criterion for the prolongation of hospitalization is also defined as an extra night at the hospital. Hospitalization may not constitute sufficient grounds to be considered as an hospitalization if it is solely for the purpose of diagnostic tests, (even if related to an AE), elective hospitalization for an intervention which was already planned before subject enrolment in the clinical trial, admission to a day-care facility, social admission (e.g., if the subject has no place to sleep), or administrative admission (e.g., for a yearly examination).

8.1.3. Unexpected adverse drug reaction

According to ICH E6, an unexpected adverse Product reaction is defined as an adverse reaction, the nature or severity of which is not consistent with the applicable trial product information (in this clinical trial: the approved Canadian product monograph at the time of AE occurrence).

8.1.4. Adverse event reporting period

The clinical trial period during which AEs must be reported is the period from when the subject signs the Informed Consent Form to the end of the subject's participation.

The sponsor should be informed if the investigator becomes aware of any unusual safety information or any safety information that appears to be drug-related involving a subject who has participated in a clinical trial, even after a subject has completed the clinical trial. The investigator should be diligent in looking for possible latent safety effects that do not appear until a medication has been discontinued.

8.1.5. Severity

Severity is a clinical determination of the intensity of an AE and not of a disease.

The investigator will classify the intensity of AEs using the following definitions as a guideline for all AEs occurring during clinical trials conducted or sponsored by *GALDERMA*. For this classification, the investigator will take into account the possible range of the intensity of the event and report the grade of intensity which is the most appropriate according his medical judgment.

Mild	Awareness of sign or symptom, but easily tolerated
Moderate	Discomfort, enough to cause interference with usual activity
Severe	Incapacitating with inability to work or perform usual activity

8.1.6. Relationship to the trial product(s) and/or clinical trial procedure

The investigator is to determine whether there is a reasonable causal relationship between the occurrence of the AE and exposure to the trial product(s) and/or clinical trial procedure required by the protocol, such as moisturizer use. AE reporting for moisturizer use should be detailed, taking into account whether moisturizer use is recommended or mandatory.

Medical judgment should be used to determine the relationship, considering all relevant factors, including pattern of reaction, temporal relationship, positive dechallenge or rechallenge, relevant medical history, and confounding factors such as co-medication or co-concurrent diseases.

The expression "reasonable causal relationship" is meant to convey in general that there are facts or arguments to suggest a causal relationship (International Conference on Harmonization (ICH) E2A, section IIIA 1).

The relationship assessment for an AE is to be completed using the following definitions as a guideline for all adverse events occurring during clinical trials conducted or sponsored by *GALDERMA*:

Reasonable possibility:

According to the reporting investigator, there is a reasonable possibility (i.e. suggestive evidence or arguments) that there is a causal relationship irrespective of the dose administered between:

- The trial product (investigational product, active comparator, or vehicle, etc.) and the AE,
- The clinical trial protocol procedure (e.g., UV-induction, biopsy, xylocaine injection, blood test or intraocular pressure measurement, ancillary products provided by the sponsor, such as moisturizers, etc.) and the AE.

The Investigator has to complete these 2 causality assessments on the AE form.

No Reasonable Possibility:

No suggestive evidence or arguments can be identified regarding a causal relationship between the investigational product or the clinical trial protocol procedure and the AE.

8.2. REPORTING PROCEDURES

8.2.1. Procedures for reporting adverse events

The collection of AEs is from the time that a subject signs the ICF to their final trial visit.

At each post-baseline visit, the investigator (or sub-investigator) will enquire about adverse events using an open question taking care not to influence the subject's answer (e.g., "Have you noticed any change in your health since the last visit?"). Direct questioning and examination will then be performed as appropriate.

Any AE occurring during the AE reporting period, whether it is related to the trial product or not, will be recorded immediately in the source document, and described in the Adverse Event Form of the eCRF along with the date of onset, severity, relationship to the trial product, and outcome, without omitting any requested and known information. Additional information will be requested under certain circumstances. Adverse Events (AEs) assessed as related to the treatment will be monitored until they are completely or satisfactorily resolved. Other AEs will be monitored until the last visit if they are not resolved or satisfactorily resolved.

Adverse events assessed as related to the treatment or trial procedure will be monitored until they have resolved or reached a stable condition. Other AEs will be monitored until the last visit if they have not resolved or reached a stable condition. The investigator will obtain and maintain in the subject's files all pertinent medical records, information and medical judgment from colleagues who assisted in the treatment and follow-up of the subject. If necessary, the investigator will contact the subject's personal physician or hospital staff to obtain further details. For SAEs (see section 8.2.2) and pregnancies (see section 8.2.3.1), the Sponsor is to be informed immediately by e-mail/fax. The event must be reported by fax or sent by e-mail to the Sponsor within 24 hours of receipt of the information (contact details in section 8.2.2).

8.2.2. Procedure for reporting a Serious Adverse Event

For an SAE occurring during the period of the clinical trial, regardless of whether it is related to the treatment or not, and of whether it is expected or not, the investigator must do the following:

1. **Take prompt and appropriate medical action**, if necessary. The safety of subject is the first priority.
2. Ensure that the event is classified as an SAE. **Immediately (no later than 24 hours) inform the Sponsor** of the event by email/ fax/, and discuss further actions to be taken:

GALDERMA R&D	
Name	[REDACTED]
Title	[REDACTED]
Address	[REDACTED] [REDACTED] [REDACTED]
Tel. during office hours	[REDACTED]
Tel. Outside office hours	[REDACTED]
Fax	[REDACTED]
Email	[contact]

3. **Complete the SAE form** provided by the CRA (Clinical Research Associate) at the start of the clinical trial (it is also available in the eCRF system as PDF document). Fax or send by email the completed form, accompanied by demographics, medical history and drugs/therapies forms (if any), and adverse event pages of the eCRF, and any other relevant information (e.g., test results) within 24 hours of receipt of the information to the Sponsor (see contact details above)
4. Print and complete the Serious Adverse Event form (available in the EDC system as PDF document). Fax or send by email the completed form, accompanied any other relevant information or anonymized medical records (e.g., laboratory test results) within 24 hours of receipt of this information to the sponsor (see contact details above). The demographics, medical history, drugs/therapies forms, and adverse event pages of the eCRF must be completed and available for review in the EDC system at the time of the report.
5. **Monitor and record the progress of the event until it resolves** or reaches a clinically stable outcome, with or without sequelae. For all additional follow-up evaluations, fax or send by e-mail all additional follow-up information on the SAE to the sponsor (see contact details above) within 24 hours of receipt of the updated information. SAEs will be monitored until the Investigator and Sponsor agree that the event is satisfactorily resolved.
6. Obtain and maintain in his/her files all pertinent medical records, information, and medical judgments from colleagues who assisted in the treatment and follow-up of the subject. If necessary, contact the subject's personal physician or hospital staff to obtain further details

7. **Inform the sponsor of the final outcome of the event.** Send a revised or updated SAE form and AE form, if appropriate.
8. Prompt notification of SAEs by the investigator to *GALDERMA* is essential so that legal obligations and ethical responsibilities towards the safety of subjects are met. *GALDERMA* has a legal responsibility to notify both the local regulatory authority and other regulatory agencies about the safety of a product under clinical investigation. *GALDERMA* will comply with country specific regulatory requirements relating to safety reporting to regulatory authorities, IRBs/IECs and investigators. Investigator safety reports are prepared for Suspected Unexpected Serious Adverse Reactions (SUSARs) according to local regulatory requirements and *GALDERMA* policy and are forwarded to investigators as necessary. An investigator who receives an investigator safety report describing an SAE(s) or other specific safety information (e.g., summary or listing of SAEs) from *GALDERMA* will file it with the Investigator's Brochure (IB) and will notify the IRB/IEC, if appropriate according to local requirements.
9. **Comply with the applicable regulatory requirements related to the reporting of SAEs to your IRB/EC.**

8.2.3. Procedure for suspected allergic contact reaction

This is a general procedure and further details can be discussed with the sponsor.

- Stop the trial product
- Take a picture of the affected area and the non-affected surrounding skin
- Document the event and report it immediately to the sponsor by email/fax, within 24 hours of receipt of the information as described in section [8.2.2](#).

In case of suspicion of allergic contact dermatitis

1. After all signs and symptoms have resolved and after a minimum of two weeks from last dose application, a re-challenge test with the assigned trial product will be performed.
2. Ensure the subject has not been under any treatment with corticosteroids or antihistamines, regardless of the route of administration, the week before testing.
3. Ensure that the skin on the back has not been exposed to the sun or artificial ultraviolet sources the week before testing.
4. Apply an appropriate quantity of the assigned trial product to fill the cupule of the test chamber on the skin of the upper back on either the right or left side of the center line (or the inner forearm if the back cannot be tested). If no test chamber is available on-site, patch test units will be provided. It may be preferable to perform the test under semi-occlusive conditions depending on the irritant potential of the trial product and the intensity of the reaction that was observed. The method to be used will be discussed with the sponsor.
5. Choose a skin site that was not previously involved in the inflammatory skin reaction.
6. Cover it for 48 hours with a hypoallergenic tape.

7. Subject should be informed about avoiding exercise, showers, application of toiletries products, etc. to keep the test system dry
8. After 48 hours, remove the tests and evaluate the site:
 - At approximately 30 minutes after patch test removal (1st reading) and,
 - 24 to 48 hours later (i.e. 72 or 96 hours after application) (2nd reading).
 - A facultative 3rd reading may be performed 96 to 120 hours later (i.e. 6 to 7 days after application of the patch) if the overall assessment so far equivocal or if asked by the sponsor.
 - Pictures of the tested areas will be taken systematically at each reading and properly documented.

Duration of trial product application	1st Reading	2nd Reading	3rd reading (optional)
48 hours	48 hours after trial product application (30 minutes after patch test removal)	72 to 96 hours after trial product application (24 to 48 hours after patch test removal)	6 or 7 days after trial product application (96 to 120 hours after patch removal)

9. Refer to the scoring system ([Spiewak R., 2008](#)) used by the International Contact Dermatitis Research Group (ICDRG) to assign a score at each reading:

Score	Morphology	Interpretation
-	No skin changes in the tested area	Negative
?	Faint, non-palpable erythema	Doubtful reaction
+	Palpable erythema (moderate edema or infiltrate), papules not present or scarce, vesicles not present	Weak positive reaction
++	Strong infiltrate, numerous papules, vesicles present	Strong positive reaction
+++	Erythema, infiltration, confluent vesicles, bullae or ulceration	Extreme positive reaction
ir	Inflammation sharply limited to the exposed area, lack of infiltrate, small petechiae, pustules, and efflorescences other than papules and vesicles	Irritant reaction
Nt		Not tested

10. At last reading, the investigator will provide an assessment regarding a possible sensitization reaction using the following scale:

Sensitization Reaction	
0	Negative (absence of reaction or might be irritant reaction)
1	Equivocal
2	Positive

11. Report the results from the re-challenge test as directed by the sponsor and document with photographs.
12. In case of absence of reaction, the subject may resume treatment if appropriate
13. If the re-challenge is positive or equivocal, notify the sponsor immediately. Except specific situations, a new series of patch test will be initiated as directed by the sponsor (with individual ingredients at different concentrations if applicable, and possibly negative and positive controls) after a minimum of additional two weeks (but not later than 6 months) and after all signs and symptoms have resolved. The patch tests will be placed on the subject's back (or the inner forearm if the back cannot be tested) distant from the site of the re-challenge test (e.g., the left upper back skin if the re-challenge test was done on the right side). Follow the same procedure for the patch test as for the re-challenge.
14. In case of suspicion of immediate contact skin reaction (such as urticaria)

A case by case approach will be applied and the procedure to follow will be discussed with the sponsor.

8.2.3.1 Procedures for reporting pregnancies

Any pregnancy occurring during clinical trials, where the foetus could have been exposed to the investigational product(s), must be followed-up until outcome in order to ensure the complete collection of safety data on *GALDERMA* product.

If a subject becomes pregnant, the Investigator is to do the following:

1. **Withdraw the subject from the clinical trial**
2. Complete all appropriate visit evaluations and eCRF pages.

Immediately (no later than 24 hours) contact the Sponsor to inform them of the pregnancy occurrence and discuss further steps to be taken:

	GALDERMA R&D
Name	[REDACTED]
Title	[REDACTED]
Address	[REDACTED] [REDACTED] [REDACTED]

Tel. during office hours	[REDACTED]
Tel. Outside office hours	[REDACTED]
Fax	[REDACTED]
Email	[contact]

3. **Complete, as fully as possible, the pregnancy surveillance form – Part I:** History and start of pregnancy - provided by the CRA at the beginning of the clinical trial (it is also available in the eCRF system as pdf document), as fully as possible. Fax or send by email this pregnancy form along with the Exit form within 24 hours of receipt of the information to the Sponsor.
4. Monitor and record the progress of the pregnancy until its outcome. Contact the subject's regular physician (general practitioner or gynecologist) or hospital staff to obtain further details and ask regular follow-up information.
5. **Inform the Sponsor of the progress by tri-monthly updates up** to the final outcome of the pregnancy. For all the additional follow-up evaluations, fax or send by e-mail the additional follow-up information to the sponsor within 24 hours of receipt of the information. If the subject can no longer be reached (lost to follow-up), documentation of the non-response/contact with two phone calls and a letter (certified with return receipt) is required.
6. **At outcome of pregnancy, complete as fully as possible the pregnancy surveillance form – Part II:** Course and outcome of pregnancy, as full as possible. Inform the Sponsor by email/ fax, then fax or send by e-mail this pregnancy form to the Sponsor within 24 hours of receipt of the information.
7. If the pregnancy leads to an abortion (voluntary abortion, spontaneous abortion or therapeutic abortion), *in utero* death or congenital anomaly, follow the procedure for declaration of an SAE (see Section 8.2.2).
8. If the investigator is informed of a developmental abnormality of the baby, even a long time after the end of the clinical trial, he/she must inform the sponsor and follow the procedure for declaration of an SAE (see section 8.2.2)

9. STATISTICAL METHODS PLANNED

9.1. STATISTICAL AND ANALYTICAL PLANS

A Statistical Analysis Plan (SAP) will be developed as a separate document. The SAP will contain a more detailed and technical description of specific data conventions, calculations and of statistical procedures for executing the analyses that are specified in the sections of the clinical trial protocol below. The SAP will be finalized prior to database lock.

Any change made to the finalized SAP will be documented in the clinical trial report.

The purpose of the trial is to evaluate subject reported outcomes with the combination of Adapalene 0.3% - BPO 2.5%, Epiduo® Forte / TactuPump™ Forte gel, after 16 weeks of treatment of moderate to severe acne in dark skin phototypes (IV to VI).

9.1.1. Variables to be statistically analyzed

The following variables will be analyzed:

Subject reported outcome variable

- *DLQI/cDLQI at Baseline, Week 12 and last visit*
- *Subject satisfaction questionnaire at Week 12 and last visit*

Efficacy variables

- *IGA score: % of subjects across scores at each visit*
- *GAI score: % of subjects across scores at Week 12 and last visit*

Safety variables on safety population

- *PIH: Raw value at each visit and % change from baseline at each post-baseline visit*
- *Local tolerance: Raw value at each visit and worst-score across visit, % of Subjects across scores at each post-baseline visit*
- *Incidence of adverse events*
- *Incidence of serious adverse events*

Other variables

- *Cosmetic acceptability questionnaire at last visit*

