Analysed variables	Subject-reported outcomes 
 • DLQI/cDLQI at Baseline and at each evaluation time • Subject satisfaction questionnaire at each evaluation time Efficacy variable 
 • IGA score: % of subjects across scores at each visit • GAI score: % of subjects across scores at Week 12 and last visit Safety variables 
 • PIH severity: Raw value at each visit and % change from baseline at each post-baseline visit • Local tolerance: Raw value at each visit and worst-score across visit, % of Subjects across scores at each post-baseline visit • Incidence of adverse events Other 
 • Cosmetic acceptability questionnaire at Week 16/Early termination 	
Principal statistical methods and sample size calculation:	
The Intent-to-Treat (ITT) population consists of all enrolled subjects. The safety population (APT) consists of the ITT population, after exclusion of subjects who never took the treatment. Population definitions will be decided before the database lock.
 
The objective of this trial is to evaluate the subject reported outcome with Adapalene 0.3% - BPO 2.5% gel during 16 weeks of treatment.
 
No inferential statistics will be performed. All variables will be descriptively summarized on ITT population and on APT population for the safety variables. The last observation carried forward (LOCF) method will be used to impute missing efficacy values.
 
As no inferential statistics will be performed, no statistical rationale of sample size can be used. However, the subject reported outcomes (quality of life and satisfaction survey), can be evaluated with a total of 60 subjects.
	

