3.2. CLINICAL HYPOTHESIS

The trial hypothesis is that daily acne treatment with Epiduo[®] Forte / TactuPump[™] Forte is well tolerated as a treatment in moderate to severe acne in dark phototypes and improves subject's quality of life.

This trial has been designed to provide evidence in support of this hypothesis.

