5.2. DISCUSSION OF CLINICAL TRIAL DESIGN

This clinical trial will assess subject reported outcomes with a product marketed in USA under the name Epiduo[®] Forte gel and TactuPump[™] Forte gel in Canada, used according to its labeling information (indication, selected population, dose regimen). Therefore, this trial will be classified as Phase IV study in USA. Meanwhile, as this product is not marketed in Mauritius and Singapore (CTD recently submitted) therefore this trial is classified as a Phase IIIb trial for Mauritius and Singapore.

According to clinical studies performed with Epiduo[®] in acne, 3 months treatment is sufficient to treat acne. As this trial aims to treat moderate to severe acne consequently, treatment period is fixed to 4 months as a maximum in order to have a complete cure of acne.

Since acne is a chronic and long-lasting skin condition which could affect seriously the psychosocial development resulting in emotional problems it is deemed important to evaluate subjects' quality of life before and after treatment.

For this subjects will complete DLQI or cDLQI for children, at baseline, Week 12 and at last trial visit.

A satisfaction questionnaire on use of the investigational product will be completed by subjects at Week 12 and at end of the trial.

An acceptability questionnaire on use of the non –investigational products will also be completed by subjects at end of the trial.

This clinical trial should allow evaluation of subjects' reported outcome after use of the investigational product Adapalene 0.3% - BPO 2.5%.

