9.1.2.3 Missing values

The last observation carried forward (LOCF) method will be used to impute missing values of global assessment scores (GAI and IGA). If no post-baseline data are available, baseline will be carried forward. Thus, the number of subjects will not vary at each visit. The other missing values will not be replaced (observed data).

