9.1.3. Data presentation and graphics

All continuous data will be summarized using usual statistics: number of values, mean, median, standard deviation, minimum and maximum, and by frequency distribution (n, %) for qualitative data. For ordinal data, both frequency distribution and usual statistics will be presented. All tables will be presented by clinical trial treatment and by visit (when applicable).

Therapies that have been stopped before the baseline visit will be presented as prior therapies. Those reported at screening or starting between screening and baseline visits and still continuing after baseline will be classified as concomitant therapies.

The adverse events will be descriptively summarized (n, %) for the safety population (APT). The adverse events will be descriptively summarized (n, %) by relationship to clinical trial treatments within System Organ Class (SOC) and preferred term (MedDRA). Subjects will be descriptively summarized (n, %) by intensity (*i.e.* mild, moderate and severe) of adverse events, SOC and preferred terms. Deaths and serious adverse events will be reported as well as withdrawals due to adverse events. A subject will be counted only once per System Organ Class (SOC) and only

once per preferred term even if more than one occurrence of an event was reported within a SOC or preferred term. In the summary by categories of intensity, the adverse event with the highest intensity will be used. The subject will be counted only once per SOC (highest intensity whatever the AE within the SOC) and once per preferred term (highest intensity whatever the AE within the preferred term).

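### Quality of life is hypothesised to improve, but no within-subject change in DLQI/cDLQI is specified, and Visit 1 lists the baseline questionnaire after the first application

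*Combined protocol and SAP*

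**What the plan says.** **The question.** Section 3.2 hypothesises that daily treatment is well tolerated "in moderate to severe acne in dark phototypes and improves" quality of life, and says the trial was designed to support this. Section 5.2 considers it important to evaluate subjects' "quality of life before and after treatment".

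**The analysis.** Section 9.1.1 lists the variable as "DLQI/cDLQI at Baseline, Week 12 and last visit", and the synopsis as "DLQI/cDLQI at Baseline and at each evaluation time". Neither mentions change. The same list in 9.1.1 has "PIH: Raw value at each visit and % change from baseline at each post-baseline visit". Section 9.1.3 plans tables by visit, Section 9.1.2.3 limits imputation to IGA and GAI, and Section 9.1.4 rules out inference. Section 9.1 defers detail to a separate SAP covering, among other things, "statistical procedures for executing the analyses that are specified in the sections of the clinical trial protocol below". It is to be final before database lock.

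**The instruments.** Section 7.1.1 and Attachment 1 give the cDLQI to subjects aged 16 or under and the DLQI to those aged 17 or over. They do not say at which visit age is taken.

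**The timing.** Section 7.1.1 requires the baseline questionnaire before the product is applied, with that word in bold. In Section 5.5.1 the supervised first application is step 18e and the questionnaire is step 19.

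**The concern.** Improvement, and before versus after, are questions about change within a subject. Separate summaries at each visit answer them only in part. If some later questionnaires are missing, the visit means describe different sets of subjects. Even with complete data, the by-visit mean and SD do not give the SD of the change or show how many subjects got better or worse.

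This matters because subject-reported outcome is the trial's stated objective and DLQI/cDLQI is the only such measure with a baseline. The satisfaction questionnaire starts at Week 12. Its improvement item is a rating of the disease made after treatment, not a measure of quality of life. With the change unnamed, which subjects, visit and instrument define it can stay open until the data of an open-label trial are in.

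The age rule adds a smaller gap. A subject who turns 17 during the 16 weeks could switch questionnaire and have no paired score.

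The Visit 1 order is a separate contradiction. Some sites may take the baseline before application and others after it.

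**Working it through.** The plan gives no figure to reproduce. Section 9.2 states 60 subjects without a calculation, and no SD, correlation, age mix or dropout rate is given for DLQI/cDLQI. Every input below except the 60 subjects and the 16 weeks is therefore an assumption, used only to show scale.

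**Who can be missing.** Under Sections 4.5.6 and 5.5.6 a subject who stops completes the next scheduled visit's procedures. A subject who stops after Week 8 therefore has the Week 12 questionnaire. The flow chart and Section 7.1.1 also require an exit questionnaire at early termination. At Week 12 the gap is limited to subjects who stop before Week 8, missed visits and subjects who cannot be evaluated. At the last visit it is limited to subjects with no exit assessment.

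**SD of the change.** With SD 6 at each visit and within-subject correlation r, SD of change = 6 × √(2(1 − r)):

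- r = 0.3: 6 × √1.4 = 7.10
- r = 0.5: 6 × √1.0 = 6.00
- r = 0.7: 6 × √0.6 = 4.65

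By-visit tables cannot tell which of these applies.

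**Paired numbers per instrument.** With 60 subjects, 20–40% aged 16 or under and 10% lacking the later value:

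- cDLQI: 0.9 × 60 × 0.2 = 10.8 (11) to 0.9 × 60 × 0.4 = 21.6 (22)
- DLQI: 0.9 × 60 × 0.6 = 32.4 (32) to 0.9 × 60 × 0.8 = 43.2 (43)

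**Information lost without pairing.** Paired 95% half-width = t(0.975, n − 1) × SD of change / √n. From by-visit n, mean and SD alone, a reader can form only t(0.975, n1 + n2 − 2) × 6 × √(1/n1 + 1/n2). At r = 0.5:

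| Instrument | Baseline n / later n | Paired | From by-visit summaries | Ratio |
|---|---|---|---|---|
| cDLQI | 12 / 11 | 4.03 | 5.21 | 1.29 |
| cDLQI | 24 / 22 | 2.66 | 3.57 | 1.34 |
| DLQI | 36 / 32 | 2.16 | 2.91 | 1.35 |
| DLQI | 48 / 43 | 1.85 | 2.50 | 1.36 |

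Over r = 0.3 to 0.7 the ratio runs from 1.09 (n = 11, r = 0.3) to 1.75 (n = 43, r = 0.7). Half-widths scale with the SD: at SD 4 to 8, the 4.03 becomes 4.03 × 4/6 = 2.7 to 4.03 × 8/6 = 5.4. The ratios do not change. No interval is planned, so these widths only illustrate the loss.

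**Shift from unmatched subjects.** If a share m lacks the later value and their baseline mean differs by d from the rest, the difference of visit means moves by m × d with no true change. With d = 4 points:

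- m = 5%: 0.05 × 4 = 0.2 points
- m = 15%: 0.15 × 4 = 0.6 points

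Divided by SD 6, this is 0.03 to 0.10 SD, in either direction. One such subject among 12 to 24 on the cDLQI moves it by 4/12 = 0.33 to 4/24 = 0.17 points.

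**Instrument switch.** If birthdays are spread evenly, 16/52 = 0.31 of subjects aged 16 at entry turn 17 during the trial. With 3 to 6 such subjects that is 0.9 to 1.8, or about 1 to 2.

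**Visit 1 order.** Steps 18e and 19 of Section 5.5.1, read in sequence, contradict Section 7.1.1. DLQI item 1 asks about itch, soreness, pain or stinging, and Section 7.3.2 defines stinging/burning as felt within five minutes of dosing, so a route to bias exists. With one-week recall and a single application the effect is probably small, but nothing in the documents allows it to be sized.

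**The case against.** **The SAP can supply it.** Section 9.1 also promises data conventions and calculations, and subtracting baseline is a calculation on two listed values. That is true. However, nothing commits the SAP to it, and the SAP need only be final before database lock.

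**Visit means and listings may suffice.** With complete data the mean change equals the difference of the visit means, and Section 10.3 provides for subject listings. The equality holds only without missing values, and a listing is not a summary of how scores changed.

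**Most variables in the list lack a change from baseline.** This is correct: IGA, satisfaction and local tolerance also have none, so the contrast with PIH alone proves little. But IGA is accompanied by GAI, which is itself a rating against baseline, and satisfaction has no baseline. Quality of life is the outcome the hypothesis says will improve.

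**Visit 1 is not strictly chronological.** Eligibility is checked at step 7, before the pregnancy test (step 9) and IGA (step 11) it depends on. Questionnaires also follow the dispensing block at Visits 4 and 5. A site could therefore comply with Section 7.1.1. The two texts still disagree, and only a site reading them together would notice.

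**The numbers are assumed and the biases small.** This stands. The case rests on a missing definition, not on a large error.

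**The total score is itself undefined.** This also stands. The document gives no item scoring and no rule for not-relevant or unanswered items.

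**Conclusion.** The concern holds on both parts. The plan poses a within-subject question and specifies only by-visit summaries for the one measure that can answer it, and the written order of Visit 1 conflicts with Section 7.1.1.

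The loss is mainly of information. Under the assumptions above, precision from by-visit summaries is about 1.3 to 1.4 times worse than paired (1.09 to 1.75 over r = 0.3 to 0.7). The bias from unmatched subjects is small, 0.2 to 0.6 points, though a single subject counts for more on the cDLQI. The instrument switch concerns perhaps 1 to 2 subjects. The effect of a post-application baseline is unknown and likely minor.

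The textual points are firm; the sizes are only as good as the assumed inputs. The matter should be fixed because the trial's central quality-of-life claim otherwise has no prespecified definition of improvement.

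**What to change.** 1. In Sections 9.1.1 and 9.1.4 and the synopsis, add: *Within-subject change from baseline in total score at Week 12 and at Week 16/early termination, in subjects with both values (paired n, mean, median, SD, minimum, maximum), tabulated separately for DLQI and cDLQI.* This stays descriptive and agrees with Section 9.1.4. A confidence interval is optional.
2. Keep each subject on the instrument used at baseline. Word the age rule as age at baseline in Section 7.1.1 and in both parts of Attachment 1.
3. In Section 5.5.1, move the baseline questionnaire (step 19) ahead of step 18.
4. Have the SAP state how each total is scored, including not-relevant and unanswered items.

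**Cost.** A few sentences, one moved step and some table rows, with no new data. The downside is a smaller n per instrument. Under the assumptions above there would be about 11 to 22 paired cDLQI and 32 to 43 paired DLQI scores, so the cDLQI change will be imprecise (half-width about 2.7 to 4.0 points at r = 0.5). About 1 to 2 subjects would complete the cDLQI after turning 17.
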